### **8.1.5. Adverse Events of Special Interest**

Not Applicable.

## **8.2. PROCEDURES FOR ELICITING, RECORDING AND REPORTING ADVERSE EVENTS**

### **8.2.1. Eliciting Adverse Events**

Data on AEs will be obtained at scheduled or unscheduled study visits, based on information spontaneously provided by the subject and/or through questioning of the subject.

To elicit AEs, questioning at each study visit should begin with simple non-leading questions. For example:

- How have you felt since your last visit?
- Have you had any health problems since you were here last?

If a subject is seen by a physician not involved with the study in relation to an AE, the Investigator should make every effort to contact the treating physician in a timely manner in order to obtain all information necessary for the appropriate reporting of the event.

### **8.2.2. Recording of Adverse Events in the eCRF**

As the quality and precision of acquired AE data are critical, Investigators should use the AE definitions provided in the above sections and should follow this guideline when completing the AE pages of the eCRF:

- Whenever possible, recognized medical terms should be used to describe AEs rather than colloquialisms (for example, 'influenza' rather than 'flu'), and abbreviations should be avoided in provided AE term.
- AEs should be described using a specific clinical diagnosis, if this is available, rather than a list of component signs or symptoms (for example, 'congestive heart failure' rather than 'dyspnoea, rales and cyanosis').
- However, signs and symptoms that are not linked (as "co-manifestations") to an identified disease or syndrome, or for which an overall diagnosis is not available, should be reported as individual AEs in separate eCRF AE page(s).
- Provisional diagnosis (e.g. "suspected Myocardial Infarction") are acceptable but should be followed up to a definite diagnosis, if finally available.
- AEs occurring secondary to other events (e.g. sequelae or complications) should be identified by the primary cause. A primary AE, if clearly identifiable, generally represents the most accurate clinical term to record in the eCRF. The Investigator should be invited to provide his/her opinion of which is the primary AE.

### **8.2.3. Reporting of Adverse Events**

Complete and accurate data on all AEs experienced for the duration of the reporting period, as defined in section 8.5, will be reported on an ongoing basis in the AE pages of the eCRF.

It is important that each AE report includes a description of the event, whether it is considered serious (and if so the criterion satisfied), its duration (onset and resolution dates), its severity, its relationship to the IMP(s), any other potential causality factors, any treatment given or other action taken (including dose modification or discontinuation of the IMP) and its outcome.

### 8.3. SERIOUS ADVERSE EVENTS

#### 8.3.1. Definitions

A Serious Adverse Event (SAE) is defined as any untoward medical occurrence or effect that at any dose:

- **results in death,**  
i.e. the AE causes or contributes to the death.
- **is life-threatening,**  
i.e. the AE places the subject at immediate risk of death; it does not refer to AE which hypothetically might have caused death if it were more severe.
- **requires inpatient hospitalization or prolongation of existing hospitalization,**  
i.e. the AE requires at least an overnight admission or prolongs a hospitalization beyond the expected length of stay. Hospital admissions for surgery planned before study entry, for social reasons, for any elective surgery (i.e. plastic surgery) or for normal disease management (including treatment adjustment) are NOT to be considered as SAE according to this criterion..
- **results in persistent or significant disability / incapacity,**  
i.e. the AE resulted in a substantial disruption of the subject's ability to conduct normal activities.
- **is a congenital anomaly / birth defect,**  
i.e. an adverse outcome in a child or fetus of a subject exposed to the IMP before conception or during pregnancy.
- **is an important medical event, i.e. is medically significant ;**

Medical and scientific judgment should be exercised in deciding whether an AE is serious in other situation. Important medical events that may not be immediately life-threatening or result in death or hospitalization but may jeopardise the subject or may require intervention to prevent one of the other outcomes listed in the definition above should also be considered serious. Examples of such events are intensive treatment in an emergency room, or at home for allergic bronchospasm, blood dyscrasias or convulsions that do not result in hospitalization, or development of drug dependency or drug abuse.

### 8.3.2. SAE Urgent Reporting Procedure

If a SAE occurs from subject consent up to week 36, with the exception of a SAE related to BMD loss which will be reported up to week 48, or, in case of study discontinuation, if the site becomes aware of an SAE up to 4 weeks post study treatment discontinuation, regardless of relationship and expectedness, the Investigator is to take prompt and appropriate therapeutic action, if necessary, to protect the safety of study subjects and report such SAE as following.

For blinded studies, refer to section 7.9. for instructions related to emergency unblinding.

The Investigator must notify **VOISIN CONSULTING** (acting on behalf of ObsEva Pharmacovigilance) **WITHIN 24 HOURS** of awareness of a new SAE or of new information on a previously reported SAE (= follow-up).

To do so, the Investigator must complete a SAE report and any specific eCRF pages if justified by the protocol e.g. AE, medical history, concomitant medication eCRF pages and blinded and anonymized copies of any other supporting source documents such as lab reports, hospital discharge letter/report, etc. ), sign it and send it directly to Voisin Consulting by e-mail using the dedicated e-mail address specified below:

**Name/Title:** Voisin Consulting / **ObsEva Pharmacovigilance**

**E-mail:** **[contact]**

**VOISIN CONSULTING** will notify ObsEva Pharmacovigilance within 1 working day after the receipt of the SAE form report or follow-up information, using the same reporting forms.

The SAE follow-up observation period, for the concerned subjects, will be jointly decided by the Investigator or one of the co-investigators (in case of Investigator's absence) and the sponsor.

In addition, the Investigator must respond to any request for follow-up information or questions regarding the SAE the sponsor may have, within 1 working day for urgent queries or 5 working days for normal queries. SAE will be followed until the Investigator and ObsEva agree that the event is satisfactorily documented and resolved/stabilized.

For any new SAE, the following minimum information is required as initial notification:

- Clear identification of the Investigator/Reporter with full contact information or site number,
- Subject identification details (study number, site number, subject's unique study identification number and date of birth),
- IMP(s) administration details (dose and dates),
- Diagnosis of the event (or a brief description of signs/symptoms/clinical course if the diagnosis is not available) and the date of onset,
- Seriousness criteria, see 8.3.1,
- Causal relationship (Investigator's opinion) of the event with the IMP(s) or with the trial procedure (e.g. the causality according to the Investigator during screening).

#### **8.4. REPORTING TO THE INDEPENDENT ETHICS COMMITTEES/ INSTITUTIONAL REVIEW BOARDS AND REGULATORY AUTHORITIES**

The Investigator must comply with any applicable requirements related to the reporting of SAEs involving the study subjects to the IEC/IRB that approved the study.

ObsEva will comply with the applicable regulatory requirements related to the expedited reporting of suspected unexpected serious adverse reactions (SUSARs) to the regulatory authorities (e.g. Health Authority, Central Ethics Committee, Central IRB). In the US, the sponsor will be responsible, through their US Agent, for notifying the FDA of any SUSAR, and the sponsor or designee is responsible for notifying the Central IRB; in the European Union (EU), the sponsor or designee is responsible for notifying the European Medicines Agency, IEC, and Competent Authorities. In regions/countries other than the US/EU, reporting of events to IECs or local authorities will be performed by the Investigator/sponsor or designee and in accordance with local procedures/regulations.

In accordance with ICH GCP guidelines, the sponsor will inform the Investigator of “findings that could affect adversely the safety of subjects, impact the conduct of the trial or alter the IEC/IRB’s approval/favourable opinion to continue the trial”. In particular and in line with respective regulations, the sponsor will inform the Investigator of AEs that are both serious and unexpected (i.e. as per the OBE2109 Investigator Brochure) and are considered by the Investigator or the sponsor, to have a reasonably possibility of causal relationship between the administered IMP and the AE (i.e. SUSAR). The Investigator will keep copies of these safety reports in the investigator’s file. National regulations with regards to safety reports notifications to Investigators will be taken into account.

Unless clearly defined otherwise by national or site-specific regulations, and duly documented, the responsible Investigator will promptly notify the concerned IEC/IRB of any safety reports provided by the sponsor and provide copies of all related correspondence to the sponsor. Only when specifically required by regulations, the sponsor (or delegate) will provide appropriate safety reports directly to the concerned IEC/IRB and maintain records of these notifications.

#### **8.5. REPORTING PERIOD**

Adverse Events (AEs) are collected on an ongoing basis from the day of signed informed consent. All new AEs and updates on all ongoing AEs or AEs with an unknown outcome, must be recorded up to week 36, with the exception of an AE related to BMD loss which will be reported up to week 48.

Protocol-related events occurring during the screening period (i.e between ICF signature and Day 1 visit) must be recorded in the eCRFs using the AE form (and SAE form if appropriate) until the date the subject is determined to be a screening failure. Beyond that date, only serious or medically relevant protocol-related events will be followed-up.

A last batch of queries will be sent after last study visit if remaining ongoing/unknown outcomes of reported AEs are pending. After the last batch of queries with all collected data have been fully processed, eCRFs and database will no longer be updated. Only SAEs and medically relevant ongoing/unknown outcome AEs will be followed-up until resolution or stabilization, under Voisin Consulting responsibility.

## 8.6. PREGNANCY AND IN UTERO DRUG EXPOSURE

Only pregnancies considered related to study treatment by the Investigator (i.e. resulting from a drug interaction) are considered as AEs.

However, **all pregnancies that are conceived up to week 36** or up to 4 weeks after the last IMP administration for subjects prematurely terminating the study must be recorded using the **Pregnancy Surveillance Form (PSF) – Part I** (History and Start of Pregnancy; PSF-part I), provided by the sponsor (or delegate) at the beginning of the study.

### Initial reporting of pregnancies:

Subjects who become pregnant during the study treatment period will be immediately withdrawn from the IMP treatment.

The Investigator must notify the sponsor in an expedited manner (same as SAE reporting) of any pregnancy occurring during the above-mentioned period, by completing the **PSF-part I**.

This form should be sent to ObsEva's Representative for Pharmacovigilance as per the same procedures and timelines described for expedited AE reporting in section 8.3.2. This form should be accompanied, as needed, by copies of the eCRF Medical History, Previous and Concomitant Therapy and the Exit Form.

### Follow-up of pregnancies:

The Investigator must actively follow-up, document and report to ObsEva's Representative for Pharmacovigilance the progress by **tri-monthly updates up to the final outcome of the pregnancy** using the **Pregnancy Surveillance Form – Part II**: (Course of Pregnancy; PSF-part II). If the subject can no longer be reached (lost to follow-up), documentation of the non-response/contact with two phone calls and a letter (certified with return receipt) are required.

Pregnancy outcomes are not recorded in the eCRF unless considered AEs.

**Pregnancy outcomes** must be reported to ObsEva's Representative for Pharmacovigilance by completing the **Pregnancy Surveillance Form – Part III**: (Course and Outcome of Pregnancy; PSF-part III). Timelines vary according to the nature of the pregnancy outcome:

- For normal outcomes, ObsEva's Representative for Pharmacovigilance should be notified within 45 days of birth/delivery.
- For abnormal outcomes, the fully completed form must be sent to ObsEva's Representative for Pharmacovigilance according to the same procedures and timelines described for expedited AE reporting in section 8.3.2. (within 24 hours of awareness of this outcome). A SAE Report form must be completed when the subject sustains an event while PSF-part III must be completed when the child/foetus sustains an event. Abnormal outcomes are defined as:
  - Abnormality of the baby (birth defect): in this case, a SAE form for the child should be completed in addition to the PSF-III.
  - Abnormality for the pregnancy (spontaneous abortion, stillbirth) or abnormality for the birth itself which could fulfil criteria of SAEs (e.g. prolongation of hospitalization due

to caesarean section complications): in this case please complete in supplement to the PSF-III a SAE form for the mother.

## 9. DATA ANALYSIS AND STATISTICS

### 9.1. TEST OF HYPOTHESES

The primary objective of the study is to assess the efficacy of a range of oral doses of OBE2109 versus placebo, in reducing overall pelvic pain in subjects with moderate to severe endometriosis pain. The corresponding primary endpoint is a 30% or greater reduction from baseline to week 12 in the mean overall pelvic pain score defined as the mean of daily pain scores reported during the preceding 4-week period assessed on a 0–3 VRS for pelvic pain.

The primary objective will be assessed by testing the following hypotheses for each active group separately:

Null hypothesis (H0): There is no difference in the proportion of subjects meeting the primary endpoint for the active treatment group compared to placebo.

$$H_0: p(\text{active}) = p(\text{placebo})$$

Alternative hypothesis (H1): There is a difference in the proportion of subjects meeting the primary endpoint for the active treatment group compared to placebo.

$$H_1: p(\text{active}) \neq p(\text{placebo})$$

Where  $p$  is the proportion of subjects with a reduction equal to or above 30% from baseline to week 12 in the mean overall pelvic pain score reported during the preceding 4-week period.

Each comparison will be carried out at the two-sided 5% level of statistical significance. No adjustment will be made for the multiple active versus placebo group comparisons (four in total: 50mg versus placebo, 75mg versus placebo, 100mg versus placebo and 200mg versus placebo) with the understanding that this increase the overall type I error rate of the study.

In addition, an overall test for dose response will be conducted using all treatment arms. The coefficients for this contrast will be defined assuming a linear response on a log (dose+1) scale.

### 9.2. SAMPLE SIZE

The planned sample size for this study is 55 subjects per treatment arm (330 subjects in total). The sample size calculation is based on pairwise comparisons for each active dose versus placebo. A two-sided type I error of 0.05, not adjusted for multiple comparisons against placebo, will be used for this exploratory study. Fifty five (55) subjects per arm will provide a power of 90% assuming a placebo response rate of 45.5% and an active treatment response rate of 76.9% (based on data from Kissei's Phase 2 study KLH1202).

### 9.3. RANDOMIZATION

Randomization will be performed via a centralized IWRS. Subjects will be randomized on Day 1 to one of six treatment groups in a 1:1:1:1:1:1 ratio for OBE2109 placebo/100mg group, OBE2109 50mg fixed-dose group, OBE2109 75mg fixed-dose group, OBE2109 100mg fixed-dose group, OBE2109 200mg fixed-dose group, OBE2109 75mg titrated-dose group, stratified by site.

Subjects will be randomized into blocks of a pre-determined length, with complete blocks being assigned to the investigational sites.

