#### 5.1.3. Study region/location

Approximately 60 investigational sites in the US and Europe will conduct the study. Potential back-up sites will be identified and qualified and will be activated in case of recruitment issue. Recruitment will be competitive between sites.

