## 6. STUDY PROCEDURES AND ASSESSMENTS

### 6.1. GENERAL INSTRUCTIONS

Before the start of the study, each subject will be provided with a subject information leaflet giving details on the Investigational Medicinal Product (IMP), study procedures and potential risks and they will also be informed verbally by the Investigator or medical delegate of the overall requirements of the study. They will be instructed that they can obtain further information from the Investigator at any time and that they are free to withdraw their consent and to discontinue their participation in the project at any time without prejudice.

If the subject is willing to participate in the study, she will be requested to give written informed consent prior to conducting any of the study screening procedures after being given sufficient time to consider her participation and the opportunity to ask for further details. Two original copies of the consent form will be signed and personally dated by both the subject and the Investigator or medical delegate. One original signed copy will be kept by the Investigator in the confidential investigator file and the second original signed copy will be given to the subject. Although nursing staff may be involved in describing the trial to a subject, the Investigator/medical delegate must participate in discussions with the subject and personally sign and date the informed consent form (ICF).

The subject will be asked if she authorizes the Investigator to notify her general practitioner of her participation in the trial.

Upon signature of the ICF, each subject will be assigned a Subject Identification Number (SIN) in the electronic Case Report Form (eCRF). Subject Identification Numbers will be made of 5 digits, as follows:

- 1st digit: country identifier (1 to 4)
- 2nd and 3rd digits: site identifier (01 to 99)
- 4th and 5th digits: subject number (01 to 99)

During the whole study, the subject will be identified using the SIN for all documentation and discussion. The SIN assigned to a subject in this way must only be used for that subject.

Should a subject drop out from the study, the SIN will not be re-allocated.

An eCRF will be completed for all subjects who signed the ICF. When a subject is subsequently not enrolled in the study, the reason for non enrollment will be recorded in the eCRF.

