#### **7.6. ASSIGNMENT TO TREATMENT GROUPS**

Prior to the start of the study, a randomization list and a treatment kit list will be generated by a designated statistician from the sponsor or delegate to be transmitted to the assigned clinical packaging organization for labelling and to a fully integrated IWRS.

Kit numbers assigned by the IWRS will start from K0001, K0002, K0003 etc. (5-characters) and will correspond to the kit number indicated on the label of the study drug.

Complete blocks of treatment materials will be assigned to the investigational sites. However, the shipment of the treatment kits (as individual 3-monthly kits) to each site will be made on an as-needed basis depending on the site screening rate.

Subjects will be randomized to one of six treatment groups in a 1:1:1:1:1:1 ratio, stratified by site.

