### **9.5.2. Primary Efficacy Analysis**

Mean overall pelvic pain scores will be calculated separately for the VRS and NRS by adding up the daily pain scores during each successive 4-week (28 day) periods and dividing by the actual number of days with non missing data (i.e. nominally 28 days if no missing data). The baseline mean overall pelvic pain score will be calculated as the mean over the two complete menstrual cycles during screening, which may not be exactly 28 days each.

The percentage of subjects with a 30% or greater reduction from baseline to week 12 (i.e. during the 4 weeks preceding week 12 time point) in the mean overall pelvic pain score will be summarized by descriptive statistics for each treatment group and overall.

The analysis of the primary endpoint will be conducted via a generalized linear model for binary data with repeated (correlated) measures, fitted using generalized estimating equations (a marginal model), with the model including terms for treatment group, 4-week period, baseline and the interactions 4-week period\*treatment, 4-week period\*baseline.

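### Randomisation is stratified by site, but the primary GEE has no site, country or region term: a minor gap to close before the Part A interim analysis

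*Combined protocol and SAP*

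**What the plan says.** Site is the only stratification factor named, and it is named twice. Section 7.6 states: "Subjects will be randomized to one of six treatment groups in a 1:1:1:1:1:1 ratio, stratified by site". Section 9.3 repeats this, ending its list of arms with "OBE2109 75mg titrated-dose group, stratified by site", and adds: "Subjects will be randomized into blocks of a pre-determined length, with complete blocks being assigned to the investigational sites". The block length is not given.

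For the analysis, section 9.5.2 says: "The analysis of the primary endpoint will be conducted via a generalized linear model for binary data with repeated (correlated) measures", fitted by generalized estimating equations, "with the model including terms for treatment group, 4-week period, baseline and the interactions" of period with treatment and of period with baseline. The synopsis gives the same list. Neither place mentions site, country or region, or explains their absence. Section 9.5 leaves further detail to a SAP to be written before the Part A interim analysis; that further text is not in the document reviewed.

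On scale, section 5.1.3 says: "Approximately 60 investigational sites in the US and Europe will conduct the study". Section 9.2 plans 330 subjects, 55 per arm. Section 6.1 gives each subject number a leading country digit running from 1 to 4, so country is already held for every subject.

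**The concern.** Stratified blocks make the arms more alike within a site than simple randomisation would. If site predicts response, the treatment estimate then varies less than an analysis blind to site assumes. Model-based standard errors come out somewhat too large, confidence intervals too wide, and tests reject a true null less often than 5%. Some efficiency that the randomisation paid for goes unused.

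The endpoint is a subjective diary response collected in two regions, so some variation between countries or sites is plausible. The document gives no figure for it. The stake is a small loss of precision in a dose-ranging study, together with the credibility of the covariate choice: section 9.6.1 gives unblinded Part A results to the sponsor, so a covariate chosen after that would not be convincingly pre-specified.

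**Working it through.** **Inputs from the protocol.** 55 per arm, 330 in total, placebo 45.5%, active 76.9%, two-sided 5%, power 90% (section 9.2); six equal arms stratified by site (9.3); about 60 sites (5.1.3); country codes 1 to 4 (6.1).

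**Assumptions, not in the document.** Size of site and country effects, blocks of six, unequal site sizes, four countries in use.

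**Step 1: the plan's own figure.** With d = 0.769 − 0.455 = 0.314 and mean rate 0.612, n = [1.96·√(2·0.612·0.388) + 1.2816·√(0.455·0.545 + 0.769·0.231)]² / 0.314² = 48.5, so 49 per arm. The continuity correction, (n/4)·[1 + √(1 + 4/(n·d))]², gives 54.7, so 55. The plan's figure reproduces. Without the correction, 55 per arm gives 93.3% power. Nothing in this calculation involves site.

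**Step 2: site size.** 330/60 = 5.5 subjects per site. A 1:1:1:1:1:1 block needs at least six, so the average site does not fill one block and balance within site is incomplete.

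**Step 3: bound under perfect balance.** If a share ρ of response variance lies between sites, the true variance is (1 − ρ) times the nominal one. The SE is overstated by the factor 1/√(1 − ρ), and null rejection is 2·[1 − Φ(1.96/√(1 − ρ))]. With se0 = √(2·0.612·0.388/55) = 0.0929, se1 = √((0.455·0.545 + 0.769·0.231)/55) = 0.0880 and f = √(1 − ρ), power is Φ[(0.314 − 1.96·se0)/(se1·f)] ignoring site and Φ[(0.314 − 1.96·se0·f)/(se1·f)] adjusting for it.

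| ρ | SE too wide by | Null rejection | Power, ignored → adjusted |
|---|---|---|---|
| 0.01 | 0.5% | 4.9% | 93.4% → 93.5% |
| 0.05 | 2.6% | 4.4% | 93.8% → 94.4% |
| 0.10 | 5.4% | 3.9% | 94.3% → 95.5% |

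**Step 4: realistic layout, one term per site.** Simulation with 4,000 runs per scenario, 60 unequal sites, blocks of six, week 12 only, one dose versus placebo. The unadjusted two-proportion test is set against a linear probability model with site fixed effects. The ICC here is on the latent logit scale, so it is not the same quantity as ρ above.

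| ICC | Nominal SE / true SD under the null | Null rejection, site ignored | Power, ignored → site dummies |
|---|---|---|---|
| 0 | 0.99 | 5.3% | 93.4% → 92.1% |
| 0.05 | 1.01 | 4.6% | 93.9% → 92.7% |
| 0.10 | 1.02 | 4.1% | 94.2% → 93.4% |
| 0.20 | 1.04 | 4.2% | 94.5% → 94.8% |

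Site dummies cost about one point of power up to ICC 0.10. With sites of equal expected size and ICC 0.10 they roughly break even (94.1% against 94.3%), and the null SE ratio is 1.04.

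**Step 5: country as the added term.** Simulation with 4,000 runs per scenario, six-arm logistic model, four countries, same layout.

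| Site SD / country SD (logit) | Null rejection, without → with country | Power, without → with | Unadjusted null SE too wide by |
|---|---|---|---|
| 0 / 0 | 4.6% → 4.6% | 93.2% → 93.2% | – |
| 0.5 / 0 | 5.1% → 5.1% | 93.7% → 93.9% | – |
| 0.5 / 0.5 | 3.9% → 4.5% | 93.7% → 94.4% | 3.6% |
| 0.7 / 0.7 | 3.2% → 3.9% | 93.8% → 95.1% | 6.4% |
| 1.0 / 0 | 3.7% → 3.8% | – | 5.9% |

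With logistic residual variance 3.29, the last three rows correspond to latent ICCs of 0.50/3.79 = 0.13, 0.98/4.27 = 0.23 and 1.00/4.29 = 0.23. The largest gain is 95.1 − 93.8 = 1.3 points. In the last row country recovers almost nothing, because the variation is purely between sites.

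**Step 6: closer to the planned model.** A six-arm simulation with a baseline covariate and robust standard errors gave 92.7% power with and without country when neither site nor country matters. At 0.5/0.5 and 0.7/0.7, null rejection moved from about 4.3% to 4.7-4.9%, and power from about 93% to 94-94.5%.

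Monte Carlo error is about 0.4 points on power. None of these runs includes the repeated measures.

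**The case against.** The strongest defence is that nothing here can mislead. The error is on the safe side. Section 9.2 calls the study exploratory, and section 9.1 knowingly accepts an inflated overall type I error across four comparisons with placebo, so a per-test rate near 4% does no harm. No ICC, site variance or regional placebo rate is given, and with moderate site effects alone the problem may be invisible: at site SD 0.5, separate simulations put null rejection anywhere between 4.0% and 5.3%. Baseline pain, already in the model, may absorb part of any site difference. Country is not the stratification factor. Part of the apparent gain may also be test size: a two-arm check with no site or country effect still showed 0.3 points more power, with null rejection rising from 4.9% to 5.2%. Finally, the covariates may yet be refined in the deferred SAP text.

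Most of this stands, and it limits the severity. It also makes omitting 60 site dummies a sound choice, since at 5.5 subjects per site they risk sparse-data and convergence trouble in a binary GEE. It does not explain why the model terms are listed twice with no mention of the stratification factor, nor does it argue against a country term that cost nothing in the six-arm simulations when irrelevant.

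A reader might infer that the standard errors are certainly too wide and that the planned power is lost. The document supports neither. The first depends on site or country being prognostic. The second fails because the 90% was computed without site, and unadjusted power stayed above 90% in every scenario.

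**Conclusion.** This is a minor specification gap. The primary model omits the only stratification factor, and any proxy for it, without giving a reason. If sites or countries differ in response, the standard errors are too wide by roughly 0-7% and null rejection is about 3.5-5% (individual simulated values 3.2% to 5.3%). Up to about 1.3 points of power are forgone relative to a model with country. If they do not differ, nothing is lost.

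The sizes rest on assumed site and country effects, blocks of six, unequal sites and four countries. The upper end needs a latent ICC of about 0.23. The stated 90% power is intact, and the plan's tests are not made anti-conservative.

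**What to change.** In section 9.5.2, the matching synopsis text and the SAP, before the unblinded Part A interim analysis:

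- Add country as a fixed main effect to the primary GEE and to the secondary repeated-measures models. State in advance when a country counts as very small, in which case US/Europe region is used instead.
- Add a sensitivity analysis that accounts for site, either with small sites pooled within country or with a random site effect. It is needed because country alone does not recover a purely site-level effect. A random-effect model is not a marginal model, so its odds ratio should be labelled as such.
- Report standardised (marginal) response proportions and their differences from the country-adjusted model. With a logit link the odds ratio becomes conditional on country, whereas the hypotheses in section 9.1 concern proportions.

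If the sponsor prefers to leave the model as it is, a sentence justifying the omission, plus the site sensitivity analysis, would be enough. The cost is up to three degrees of freedom and a few lines of text. No new data are required, and section 9.5 already schedules the SAP before the interim analysis.
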